3 SUBJECT POPULATIONS

3.1 Population Definitions

The following subject populations will be evaluated and used for presentation and analysis of the data:

Enrolled subjects: subjects who sign an informed consent form and are assigned a subject identification number.

Randomized subjects: enrolled subjects who receive a randomization treatment assignment from the interactive web response system (IWRS).

Treated subjects: enrolled subjects who take any amount of study therapy (rimegepant or placebo).

Modified Intent-to-Treat (mITT) subjects: enrolled subjects who are randomized only once, take study therapy, have a baseline migraine of moderate to severe intensity, and who provide at least one post-baseline efficacy data point.

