Freedom from nausea, freedom from phonophobia, freedom from photophobia, and FDS response will be tabulated by treatment group at each post-dose time point. The tabulation will include: the total number of subjects reporting each of the above symptoms at baseline, success as the percentage of the total number of subjects reporting the symptoms at baseline, and the number of subjects that reported the symptom but with missing data at the post-dose time point as a percentage of the number reporting the symptom at baseline.

4.7.5.6 *Pain Freedom to 8 Hours Post-Dose*

Pain freedom over time up to 8 hours will be analyzed using Kaplan-Meier methods. Kaplan-Meier estimates will be tabulated using the following time periods (0 through 15 minutes, >15 through 30 minutes, > 30 through 60 minutes, > 60 through 90 minutes, > 90 through 120 minutes, >120 minutes through 180 minutes, >180 minutes though 240 minutes, >240 minutes though 360 minutes, >360 minutes though 495 minutes, and > 495 minutes). For each time period, the number of subjects at risk, with an event (pain freedom), censored, and survival

probability estimate (with 95% CI), will be presented by treatment group. Subjects who fail to reach no pain by 495 minutes, will be censored at 496 minutes. Additionally, subjects who take rescue medication prior to 495 minutes will be censored at the date/time associated with their rescue medication. Note that the probability of survival corresponds to the probability of NOT having pain freedom. Survival estimates are calculated using the Kaplan-Meier product-limit method and median survival (time to pain freedom), and will be presented along with 95% CIs calculated using the method of Brookmeyer and Crowley.

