To support the analysis, a Kaplan-Meier plot, with time in minutes on the x-axis and probability of survival on the y-axis, will be presented by treatment group. The number at risk at each time point (0, 15, 30, 45, 60, 90, 120, 180, 240, 360, and 495) minutes will be presented below the figure. In this analysis, being at risk corresponds to not yet having achieved pain freedom; therefore, the subject is still “at risk” of having pain freedom. Once a subject has pain freedom or is censored, then the subject is no longer in the risk pool. If a subject has missing data at an earlier time point, then the time point with missing data is not considered. The subject is still considered at risk of failure at a future time point if data are available. Subjects are censored as described above.

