2.2.1 Kaplan-Meier Plots and Tables: Actual Time for Event of Interest

The first set of K-M plots and tables were created using actual time of censoring and actual time for the clinical event of interest. Subjects were censored at the actual time of their first use of rescue medication or last reported data point if lost to follow-up. Subjects who did not have the clinical event of interest by 8 hours post dose were censored at 496 minutes (480 minutes + 15 minute window + 1 minute).

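### The Kaplan-Meier analyses of pain relief and pain freedom set no censoring time for subjects who stop the diary; read literally, they stay at risk to 496 minutes, which overstates time to response

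*SAP*

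**What the plan says.** SAP 4.7.5.2 (pain relief) and 4.7.5.6 (pain freedom) share one set of rules for the curve up to 8 hours.

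- No event: "Subjects who fail to reach no pain by 495 minutes, will be censored at 496 minutes".
- Rescue: "Additionally, subjects who take rescue medication prior to 495 minutes will be censored at the date/time associated with their rescue medication".
- Gaps in the diary: "If a subject has missing data at an earlier time point, then the time point with missing data is not considered". Then: "The subject is still considered at risk of failure at a future time point if data are available". The paragraph closes by referring back to the two censoring rules above.

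Neither section gives a censoring time for a subject who makes no further entries. In 4.7.5.6 the scale of the curve is stated: "Note that the probability of survival corresponds to the probability of NOT having pain freedom". In 4.7.5.2 the event should be pain relief, but the censoring rule, the event column and the median are worded in terms of no pain or pain freedom.

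SAP 3.1 admits to mITT subjects "who provide at least one post-baseline efficacy data point", so one entry at 15 minutes is enough.

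SAP Appendix 3, section 2.2.1, on absence of MBS, nausea, photophobia and phonophobia and on return to normal functioning, reads: "Subjects were censored at the actual time of their first use of rescue medication or last reported data point if lost to follow-up". Section 2.2.2 repeats this for nominal times. Section 2.1, on time to rescue, also ends risk at loss to follow-up.

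**The concern.** A Kaplan-Meier risk set should hold only subjects in whom an event could still be observed. Under the literal rule, someone whose last entry is at 90 minutes, without response or rescue, counts as an observed non-responder at every later time point. That enlarges the denominators, pushes the survival curve up and delays the median. If drop-out differs between arms, the comparison shifts as well.

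The protocol synopsis names time to onset of action among the information to be obtained. SAP Appendix 1 marks the outputs as topline: Tables 14.2.3.3.1, 14.2.3.3.2, 14.2.3.13.1 and 14.2.3.13.2, and Figures 14.2.8 and 14.2.9. They would be read beside the Appendix 3 curves for MBS and normal functioning, which treat the same kind of subject differently.

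**Working it through.** **The plan's own figure.** Appendix 3, 2.2.1 has subjects "censored at 496 minutes (480 minutes + 15 minute window + 1 minute": 480 + 15 + 1 = 496. It reproduces. It is an administrative end point for subjects followed through the 8-hour window.

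**Direction.** Take 10 subjects at risk. Two stop the diary without response, then four respond. Literal rule: 4/10 = 40%. Censoring the two at their last entry: 4/8 = 50%. The literal rule lowers response and so lengthens time to response.

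**Size, closed form.** The documents give no diary drop-out rate, so the inputs below are assumptions unless marked.

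- S2 = share event-free at 2 hours
- q = probability that these respond between 2 and 8 hours
- m = share of these with no later entry
- Literal 8-hour cumulative response = 1 − S2 × (1 − q × (1 − m)), so the loss is S2 × q × m
- No rescue censoring; drop-outs respond like the others; all drop-out falls at 2 hours

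| S2, q | m = 0 | m = 5% | m = 10% | m = 15% |
|---|---|---|---|---|
| 0.80, 0.60 | 68.0% | 65.6% | 63.2% | 60.8% |
| 0.85, 0.50 | 57.5% | 55.4% | 53.3% | 51.1% |

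In the first row the losses are 2.4, 4.8 and 7.2 points. The Phase 2b pain-freedom rates in Protocol 1.3.2 (31.4% and 15.3%) give S2 of 0.686 and 0.847, so 0.80 lies between them.

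For pain relief, the Phase 2b rates of 72.1% and 51.2% give S2 of 0.279 and 0.488. With the same q = 0.60:

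- rimegepant: 0.279 × 0.60 × 0.05 = 0.8 points, and 1.7 points at 10%
- placebo: 0.488 × 0.60 × 0.05 = 1.5 points, and 2.9 points at 10%

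**Unequal drop-out.** With identical true curves (S2 = 0.80, q = 0.60), 5% drop-out on rimegepant and 10% on placebo give 65.6% against 63.2%, a spurious 2.4 points in favour of rimegepant.

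**Size, simulation.** Exponential response times were calibrated to the Phase 2b 2-hour rates, with non-informative drop-out spread evenly in hazard to reach 5% or 10% by 8 hours, no rescue censoring, and 400,000 draws per scenario. Each cell shows last-entry censoring, then the literal rule.

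| Curve | Median (min), 5% | Median (min), 10% | 8-hour response, 5% | 8-hour response, 10% |
|---|---|---|---|---|
| Pain freedom, rimegepant | 220, 224 | 221, 229 | 0.789, 0.774 | 0.788, 0.757 |
| Pain freedom, placebo | not reached in either | not reached in either | 0.495, 0.484 | 0.497, 0.474 |
| Pain relief, rimegepant | 65, 65 | 65, 66 | 0.995, 0.986 | 0.995, 0.975 |
| Pain relief, placebo | 116, 117 | 116, 118 | 0.949, 0.935 | 0.948, 0.920 |

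The 8-hour losses here are 0.9 to 3.1 points, below the closed-form 2.4 to 4.8, because drop-out is spread over time. With an equal 10% drop-out, the between-arm difference in pain freedom barely moves: 0.788 − 0.497 = 0.291 against 0.757 − 0.474 = 0.283. At 30% drop-out the rimegepant pain-freedom median goes from 221 to 248 minutes.

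**The case against.** The best defence is textual. The sentence "The subject is still considered at risk of failure at a future time point if data are available" can be read to mean that a subject without later data is no longer at risk. One can add that a subject who stopped answering has not been shown to fail by 495 minutes. This stands in part: the text is ambiguous rather than plainly wrong. But it offers no alternative censoring time and then sends the reader back to the two stated rules, so two programmers could draw different curves.

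A second defence is that holding drop-outs as non-responders is conservative and in the spirit of NC=F. That fits poorly here. These curves censor rescue users instead of counting them as failures, so a subject known to need rescue leaves the risk set while one with no data stays in it.

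The objections to size are fair. Drop-out is unknown, and rescue from 2 hours already removes many non-responders. If drop-outs would never have responded, this bias disappears.

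Three stronger readings are tempting and not supported:

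- A reader might infer that time to response is understated, so that the rule flatters the drug. The direction is the reverse in each arm; only unequal drop-out could favour one arm.
- A reader might infer that the SAP gives two rules for one analysis. Appendix 3, section 2.2 does not list pain relief or pain freedom, so this is an inconsistency between sections.
- A reader might infer that the trial's main conclusions are at risk. SAP 4.2.5 and 4.7.5 keep exploratory p-values descriptive, 4.7.5.2 and 4.7.5.6 specify no between-group Kaplan-Meier test, and 4.7.5.5 tabulates binary results at every time point separately.

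**Conclusion.** The point holds as a minor one. SAP 4.7.5.2 and 4.7.5.6 need a censoring time for subjects whose diary stops. The literal rule overstates time to response and understates cumulative response, provided drop-outs could still respond. At an assumed 5% to 10% drop-out the effect on 8-hour response is a few points at most, and medians shift by 0 to 8 minutes in the simulated scenarios where a median is reached. How large it would be in this trial cannot be told from the documents. Co-primary and secondary results do not use these curves and are unaffected.

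**What to change.** In both sections replace the censoring sentences with: *Subjects without the event are censored at first rescue medication if taken before 495 minutes; otherwise at 496 minutes if the 8-hour diary entry is present; otherwise at the last diary entry made before the 8-hour time point.* Apply the same rule to the number-at-risk rows.

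Align Appendix 3, 2.2.1 and 2.2.2 for a subject who misses the 8-hour entry but answers later. Such a subject is not clearly lost to follow-up, and the present wording could send them to 496 minutes.

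In 4.7.5.2 name pain relief as the event throughout, in place of no pain and pain freedom.

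One gap remains, as it does in Appendix 3: a subject whose diary stops well before rescue is at risk until rescue. The sponsor should state whether that is intended.

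The cost is a short SAP edit, a small programming change and slightly wider confidence intervals at later times.

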4.8 Pharmacokinetic Evaluation

No pharmacokinetic data will be collected in this study.

4.9 Safety Evaluation

Safety analyses will be conducted on the treated population by as-treated treatment group (i.e., the actual treatment received) and overall. All safety data will be presented in by-subject listings and will indicate which values are on-study or on-treatment.

Safety outcome measures include: AEs, laboratory assessments including liver toxicity, vital signs, physical measurements, electrocardiograms (ECGs), concomitant and rescue medications, and suicidal ideation and behaviors. Unless otherwise noted, baseline is considered as last non-missing assessment on or prior to study drug randomization.

4.9.1 Extent of Exposure

Extent of exposure is measured by subjects providing self-reported study drug exposure information in their eDiaries. As a check on this exposure data, study drug accountability data are provided by the study center on the “Drug Accountability” CRF page.

The self-reported study drug exposure data will be tabulated by treatment group and overall for randomized subjects who had an on-study migraine, and will include:

- The number (and percentage) of randomized subjects that took study medication
 - The number and percentage who took the medication prior to providing baseline study migraine characteristics

- The number and percentage that took study medication after providing baseline study migraine characteristics
- The number and percentage of randomized subjects who reported not taking study medication
- The number and percentage of randomized subjects for whom no exposure data was reported

The study drug accountability will be tabulated by treatment group and overall for randomized subjects who had an on-study migraine, and will include:

- The number and percentage of randomized subjects to whom kits were dispensed
- The number and percentage of kits returned
 - The number and percentage of kits returned from which the IP was used
 - The number and percentage of kits returned from which the IP was not used
- The number and percentage of kits not returned

A cross tabulation of exposure and accountability data will be prepared. This will be done overall for randomized subjects who had an on-study migraine. For the exposure and accountability data, the categories are: Took IP, Did not Take IP, and Unknown.

A by-subject listing will be prepared that indicates the study drug exposure and accountability status of all randomized subjects. A patient identifier (PID) listing will be prepared if subjects had unknown exposure data, unknown accountability data, or for whom the exposure and accountability data did not match.

4.9.2 Adverse Events

AEs will be coded using MedDRA and displayed in tables and listings by SOC and PT, unless specified otherwise.

On-study AEs are those with a start (onset) date on or after the randomization date.

Adverse events are summarized by subject incidence rates; therefore, in any tabulation, a subject contributes only once to the count for a given AE (SOC or PT). The number and percentage of subjects with any on-study AE, with any on-study AE related to treatment (unlikely related, possibly related, or related), with any on-study SAE, with any on-study SAE related to treatment, with any on-study severe AE, with any on-study AE leading to study drug discontinuation and with any on-study AE leading to death will be summarized by treatment group and overall.

The number and percentage of subjects with on-study AEs will also be summarized by SOC and PT for the following: any AE; AEs related to study drug; SAEs; severe AEs; and AEs leading to study drug discontinuation. AEs will be displayed in descending order of overall frequency within SOC and PT.

In these tabulations, each subject will contribute only once (i.e., the most related occurrence or the most intense occurrence) to each of the incidence rates in the descriptive analysis, regardless of the number of episodes. All AEs will be listed and indicate whether or not the AE was serious, occurred on study, or potentially occurred on treatment. Additional listings will be provided including: deaths; SAEs; and AEs leading to study drug discontinuation.

Potentially on-treatment AEs are those with a start date on or after the first dose of study drug date. Given that the AEs do not have recorded onset times, these on-study events are considered to be potentially on-treatment. (Thus, potentially on-treatment AEs are a subset of on-study AEs).

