9.4.3 Analysis of Safety

The investigators determine the intensity of AEs and the relationship of AEs to study therapy. The investigators' terms are coded and grouped by system organ class using the latest version of the Medical Dictionary for Regulatory Activities (MedDRA) available. AEs are presented by system organ class and preferred term, ordered by the overall frequency of events. If a subject had an adverse event with different intensities over time, then only the greatest intensity is reported.

AEs are tabulated in all treated subjects. SAEs occurring in subjects enrolled but not treated are listed. Deaths are listed for enrolled subjects without regard to onset.

The frequencies of the following safety events are summarized by treatment regimen, and overall, for treated subjects: SAEs; all AEs, non-serious AEs, AEs by intensity; and AEs by relatedness.

Graphical and tabular displays of liver function test results are provided.

Further safety analyses will be described in the statistical analysis plan.

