14.2.3.8	Freedom from Most Bothersome Symptom at Every Timepoint Post Dose: Exploratory Analysis	mITT Subjects	Y
14.2.3.9	Freedom from Photophobia at Every Timepoint Post Dose: Exploratory Analysis	mITT Subjects	
14.2.3.10	Freedom from Phonophobia at Every Timepoint Post Dose: Exploratory Analysis	mITT Subjects	

Table Number	Title	Population	Topline
14.2.3.11	Freedom from Nausea at Every Timepoint Post Dose: Exploratory Analysis	mITT Subjects	
14.2.3.12	Functional Disability Scale at Every Timepoint Post Dose: Exploratory Analysis	mITT Subjects	Y
14.2.3.13.1	Kaplan-Meier Time to First Report of Pain Freedom up to 8 Hours Post Dose: Exploratory Analysis	mITT Subjects	Y
14.2.3.13.2	Median Time to First Report Pain Freedom: Exploratory Analysis	mITT Subjects	Y
14.3.1.1	Self-Reported Study Drug Exposure Summary	All Randomized Subjects who had a Study Migraine	
14.3.1.2	Study Drug Accountability Summary	All Randomized Subjects who had a Study Migraine	
14.3.1.3	Cross Tabulation of Study Drug Exposure and Accountability	All Randomized Subjects who had a Study Migraine	
14.3.2.1	Summary of On-Study Adverse Events	Treated Subjects	Y
14.3.2.2	Incidence of On-study Adverse Events by System Organ Class and Preferred Term	Treated Subjects	Y
14.3.2.3	Incidence of On-study Adverse Events Related to Study Drug by System Organ Class and Preferred Term	Treated Subjects	
14.3.2.4	Incidence of On-study Serious Adverse Events by System Organ Class and Preferred Term	Treated Subjects	Y
14.3.2.5	Incidence of On-study Adverse Events with Severe Grade by System Organ Class and Preferred Term	Treated Subjects	Y
14.3.2.6	Incidence of On-Study Adverse Events Leading to Study Drug Discontinuation by System Organ Class and Preferred Term	Treated Subjects	
14.4.1.1	Hematology (SI Units): Observed and Change From Baseline Values by Visit	Treated Subjects	
14.4.1.2	Hematology (UI Units): Observed and Change From Baseline Values by Visit	Treated Subjects	
14.4.2.1	Serum Chemistry (SI Units): Observed and Change From Baseline Values by Visit	Treated Subjects	
14.4.2.2	Serum Chemistry (US Units): Observed and Change From Baseline Values by Visit	Treated Subjects	
14.4.3	Hematology: Shift from Baseline by Visit	Treated Subjects	
14.4.4	Serum Chemistry: Shift from Baseline by Visit	Treated Subjects	
14.4.5	Urinalysis: Shift from Baseline by Visit	Treated Subjects	
14.4.5.2	Urine Drug Screen: Shift from Baseline by Visit	Treated Subjects	

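### AE tables count from randomization, so none gives rates after the single dose, and the protocol's by-intensity and non-serious AE summaries are cut to severe only or absent.

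*SAP*

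**What the plan says.** **Counting window.** SAP 4.9.2 starts the on-study class at randomization: "On-study AEs are those with a start (onset) date on or after the randomization date". That class feeds the overview and all five summaries by system organ class and preferred term. In Appendix 1, Tables 14.3.2.1 to 14.3.2.6 are all titled on-study and use treated subjects. Two examples are "Incidence of On-study Adverse Events by System Organ Class and Preferred Term" (14.3.2.2) and "Incidence of On-study Adverse Events Related to Study Drug by System Organ Class and Preferred Term" (14.3.2.3).

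**Post-dose class.** The same section defines a narrower class: "Potentially on-treatment AEs are those with a start date on or after the first dose of study drug date". Its only stated use is in a listing: "All AEs will be listed and indicate whether or not the AE was serious, occurred on study, or potentially occurred on treatment". No table in Appendix 1 or Appendix 4 reports it.

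**Timing.** Subjects hold the dose for up to 45 days after randomization (Protocol 4.3.2) and return within 7 (+2) days of treatment (Protocol 4.3.4). Collection of non-serious AEs begins at the Baseline visit (Protocol 8.2.1).

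**Promised summaries.** For treated subjects, Protocol 9.4.3 lists "SAEs; all AEs, non-serious AEs, AEs by intensity; and AEs by relatedness". On intensity, the SAP offers a severe row in the overview and Table 14.3.2.5, "Incidence of On-study Adverse Events with Severe Grade by System Organ Class and Preferred Term". It has no non-serious AE summary. Exploratory objective 7 (SAP 1.2.3) names three measures: AEs of moderate intensity or worse, serious AEs, and laboratory abnormalities.

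**The concern.** In a single-dose trial the safety question is what happens after the tablet is taken. A treated subject's AE from the waiting period, before any drug, enters the tables on the same footing as one that follows the dose. The tabulated percentages therefore describe a mixture of the two periods, and a reader who wants the post-dose profile by arm must rebuild it from a listing of about 1,200 treated subjects (2 × 600).

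The related-AE rows help only in part, because they count subjects "with any on-study AE related to treatment (unlikely related, possibly related, or related", so an event judged unlikely to be related still counts as related.

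The second gap needs no modelling. Two summaries to which the protocol commits would not be produced, and one of the three measures in objective 7 would have no table.

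**Working it through.** **1. Commitments set against tables**

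| Protocol 9.4.3 summary | SAP 4.9.2 and Appendix 1 |
|---|---|
| Serious AEs | Overview row, Table 14.3.2.4 |
| All AEs | Overview row, Table 14.3.2.2 |
| Non-serious AEs | None |
| AEs by intensity | Severe only: overview row, Table 14.3.2.5 |
| AEs by relatedness | Related only: overview row, Table 14.3.2.3 |

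A non-serious count cannot be had by subtracting subjects with a serious AE from subjects with any AE, because one subject may have both. A severe-only table cannot yield moderate-or-worse.

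**2. Share of counted time that precedes the dose (illustrative)**

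The documents assume that roughly 85% of 715 per arm have a migraine in time (SAP 4.1): 0.85 × 715 = 607.75, consistent with the stated figure of about 600. They give no distribution of waiting times, so I assume an exponential wait cut off at 45 days, with daily rate λ:

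- Mean wait in dosed subjects = 1/λ − 45·exp(−45λ) / (1 − exp(−45λ))
- Pre-dose share = wait / (wait + f), with f = 7 days of follow-up

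Two ways to set λ:

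- Matched to 85% dosed: λ = −ln(0.15)/45 = 0.04216 per day. This equals 30 × 0.04216 = 1.26 treated attacks per 30 days, below the eligibility minimum of 2 per month. It therefore implies that attacks go untreated, and it gives the longest waits. Using 600/715 instead gives 16.0 days and 70%.
- From attack frequency: λ = k/30 for k = 2, 4 and 8. The eligibility limits are 2 and 8 (Protocol 5.2, criteria 2c and 2e).

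**3. Background percentage, on-study against post-dose**

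The documents give no AE rates. I assume a constant background hazard b of 0.2%, 0.6% or 1.0% a day, captured equally before and after dosing.

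- Post-dose: p = 1 − exp(−7b)
- On-study: 1 − E·(1 − p), with E = [λ/(λ+b)] · [1 − exp(−45(λ+b))] / [1 − exp(−45λ)]

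For b = 0.2%, 0.6% and 1.0%, p is 1.4%, 4.1% and 6.8%. With the 85%-matched wait, the on-study figures are 4.4%, 12.6% and 19.8%.

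| Wait model | Mean wait (days) | Pre-dose share | On-study ÷ post-dose |
|---|---|---|---|
| 8 attacks per 30 days | 3.75 | 35% | 1.5 |
| 4 attacks per 30 days | 7.39 | 51% | 2.0 |
| 2 attacks per 30 days | 12.64 | 64% | 2.6 to 2.8 |
| Matched to 85% dosed | 15.78 | 69% | 2.9 to 3.2 |

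With f = 9 days, the share for the 85%-matched wait is 15.78/24.78 = 64%.

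**4. What happens to a drug–placebo contrast**

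Assume the drug adds a post-dose AE with probability 0.05. The risk difference is then 0.05 × (1 − background).

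- Post-dose: 0.05 × (1 − 0.0139) = 4.9 points down to 0.05 × (1 − 0.0676) = 4.7 points.
- On-study: 4.9 points (8 attacks, b = 0.2%) down to 0.05 × (1 − 0.1982) = 4.0 points (85%-matched, b = 1.0%).

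Take b = 0.6% with the 85%-matched wait as an example. The percentages are 4.11% and 8.90% post-dose (ratio 2.17), against 12.55% and 16.92% on-study (ratio 1.35). With 600 per arm, the standard error of the difference is √[(0.0411 × 0.9589 + 0.0890 × 0.9110)/600] = 1.4 points post-dose and √[(0.1255 × 0.8745 + 0.1692 × 0.8308)/600] = 2.0 points on-study.

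**The case against.** The case against the first part has weight. The protocol collects non-serious AEs from Baseline and sets no post-dose window in 9.4.3, so the SAP tabulates what is collected. The authors did not overlook post-dose events: they defined the class, explained that missing onset times make it only potential, and flagged it in the listing. Counting from randomization also fits the cautious handling of partial dates in SAP 4.2.7. The tables are limited to treated subjects, so never-dosed subjects do not enter.

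A reader might infer that the tables favour one arm, or that they hide a drug effect. The documents support neither. Randomization balances pre-dose events on average. SAP 4.9.2 plans counts and percentages with no AE test or risk ratio, and the difference in percentages largely survives. Non-serious AEs from the treatment period are reported at the End of Treatment visit (Protocol Table 1, footnote 7), so poorer recall of earlier events would shrink the inflation further.

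What stands is that a listing flag is not a rate by arm, and the tabulated percentages would overstate how often treated subjects have AEs after the dose.

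On the second part, one could say that the severe table partly covers intensity, that non-serious AEs are a subset of Table 14.3.2.2, and that objective 7 is exploratory. These points limit the gap without closing it. Protocol 9.4.3 has the greatest intensity reported when a subject's intensities differ, which presupposes several levels. Its closing remark that the SAP will describe further safety analyses adds to the list and withdraws nothing from it.

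**Conclusion.** Both parts hold, with different force.

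The missing summaries are a plain mismatch between protocol and SAP and rest on no assumption. Objective 7 is not wholly without output: its serious AE and laboratory measures are covered, and only moderate-or-worse intensity has no table.

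The counting window is an analysis choice that leaves a gap. It is not an error against the protocol and not a source of bias between arms. With 7 days of follow-up, about 35% to 70% of the counted time would precede the dose, and background percentages would be about 1.5 to 3 times the post-dose ones. The upper end needs waits longer than the eligibility minimum attack frequency implies. An assumed 5-point excess would move from 4.7–4.9 to 4.0–4.9 points, estimated against more background noise. These sizes depend on the exponential wait, the assumed daily AE rates and equal capture before and after dosing. That no post-dose table is planned does not depend on them.

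**What to change.** In SAP 4.9.2 and Appendix 1:

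- Add an AEs-by-intensity table with a moderate-or-worse row, and the protocol's non-serious AE summary.
- Add on-treatment versions of Tables 14.3.2.1, 14.3.2.2 and 14.3.2.3, counting AEs that start on or after the dose date. Keep the on-study tables.
- Footnote that events earlier on the dosing day cannot be separated, because onset times are not recorded.

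In SAP 4.2.7, extend the partial-date rule, which now compares AE starts with randomization only, to the dose date: count an AE as on-treatment unless it can be shown to have started before dosing.

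The cost is SAP wording, one added date rule and about five more tables (three on-treatment, one by intensity, one non-serious), all from data already collected. The split on the dosing day stays imperfect.

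### SAP 4.9.2 counts AEs judged unlikely related as treatment-related in one merged class, and no planned table is stated to show the relatedness levels

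*SAP*

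**What the plan says.** Protocol 9.4.3 leaves causality to the sites: "The investigators determine the intensity of AEs and the relationship of AEs to study therapy". Among the frequencies to be summarised by regimen and overall in treated subjects it lists "SAEs; all AEs, non-serious AEs, AEs by intensity; and AEs by relatedness". It names neither the levels nor the scale.

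SAP 4.9.2 defines relatedness once, in the list of rows for the overall AE summary: subjects "with any on-study AE related to treatment (unlikely related, possibly related, or related"). A related-SAE row follows with no definition of its own. The same section then names the breakdowns by system organ class and preferred term: "any AE; AEs related to study drug; SAEs; severe AEs; and AEs leading to study drug discontinuation". It adds a counting rule under which "each subject will contribute only once (i.e., the most related occurrence or the most intense occurrence").

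SAP Appendix 1 carries this through as Table 14.3.2.1, "Summary of On-Study Adverse Events", marked topline, and Table 14.3.2.3, "Incidence of On-study Adverse Events Related to Study Drug by System Organ Class and Preferred Term", not marked topline. No title in the table list mentions relatedness levels.

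**The concern.** An investigator who marks an event *unlikely related* has judged that the drug is probably not the cause. The SAP puts that judgement under the same label as *possibly related* and *related*, and does not say why. Two things follow.

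First, the headline percentage of subjects with a treatment-related AE may be higher than the percentage for whom an investigator thought the drug a possible or actual cause. Table 14.3.2.1 is a topline table, so this figure will be read early.

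Second, the protocol's summary by relatedness shrinks to one merged class. A reader of the planned rows cannot tell how much of it is *unlikely*, or whether that part is balanced between the arms.

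**Working it through.** **Text comparison**

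| Item | Protocol 9.4.3 | SAP 4.9.2 and Appendix 1 |
|---|---|---|
| Display | AEs by relatedness, by regimen and overall | One merged related class in the overview; one related-AE table by class and term |
| Levels | Not named | Three named, all counted as related |
| Related SAEs | Not separately mentioned | A row with no definition of its own |
| Reason for the cut | None | None |

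The parenthesis belongs to the AE overview row. Applying it to the related-SAE row and to Table 14.3.2.3 is an inference: no other definition is given, but the SAP does not say that this one carries over.

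**Direction of the effect**

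The documents state no related-AE rate, so there is no planned figure to reproduce. In one arm, let r be the proportion of subjects with a possibly related or related AE, and v the proportion whose most related AE is only *unlikely related*. The SAP row shows m = r + v.

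- m ≥ r, with equality only if v = 0.
- With u = v/m, m/r = 1/(1 − u). If u = 0.2 the factor is 1/0.8 = 1.25; if u = 0.5 it is 1/0.5 = 2.0. Both values of u are assumptions.
- Difference between arms: (r₁ + v₁) − (r₀ + v₀) = (r₁ − r₀) + (v₁ − v₀). If v is balanced, the difference is unchanged.
- Ratio with balanced v: (r₁ + v)/(r₀ + v), which moves toward 1 as v grows.

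**Illustration on assumed rates**

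Inputs: about 600 treated per arm (SAP 4.1; 0.85 × 715 = 607.75); r₁ = 6% and r₀ = 3% (assumed); v equal in both arms (assumed).

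| v per arm | Row shows | Subjects of 600 | Difference | Ratio |
|---|---|---|---|---|
| 0% | 6% vs 3% | 36 vs 18 | 3 points | 2.00 |
| 1% | 7% vs 4% | 42 vs 24 | 3 points | 1.75 |
| 2% | 8% vs 5% | 48 vs 30 | 3 points | 1.60 |
| 5% | 11% vs 8% | 66 vs 48 | 3 points | 1.38 |
| 10% | 16% vs 13% | 96 vs 78 | 3 points | 1.23 |

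With assumed rates of 5% versus 4%, the ratio goes from 1.25 at v = 0% to 1.07 at v = 10%, and the difference stays at 1 point.

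The unchanged difference is less precise. Its standard error is √[(p₁(1 − p₁) + p₀(1 − p₀))/600]. At 6% versus 3% this is √[(0.0564 + 0.0291)/600] = 1.19 points; at 8% versus 5% it is √[(0.0736 + 0.0475)/600] = 1.42 points.

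**The case against.** The strongest reply is that the rule is disclosed and can be conservative. The SAP states which levels count as related. Counting every event not ruled out raises the sponsor's own attributed rate, and it keeps any true drug effect that an investigator wrongly called unlikely. Neither document defines the causality scale, so where to cut it is a convention. This stands: the inclusive definition is not an error in itself.

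A reader might infer that the SAP breaks a protocol promise to show every level. The protocol does not support that. It says only AEs by relatedness, names no levels, and leaves further safety analyses to the SAP. The SAP treats intensity in a similar way, planning tables of severe AEs. A breakdown is the natural reading, and the most-related-occurrence rule would suit one, but it is not a literal requirement.

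A reader might also infer that the levels cannot be recovered. That goes too far. SAP 4.9 promises by-subject listings of all safety data, Appendix 1 includes AE and SAE listings (16.2.7.1 and 16.2.7.2), and the appendix gives table titles rather than shells. Even so, the AE listing described in 4.9.2 does not mention relatedness, and a hand count from listings does not replace a summary.

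Finally, a reader might infer that the merged class hides a drug signal. The documents do not show this. With balanced *unlikely* events the difference does not move, the SAP plans no AE ratio, and Table 14.3.2.2 compares all AEs by class and term whatever the causality judgement.

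**Conclusion.** The point holds in limited form. The row labelled as related to treatment is at or above the possibly-or-related percentage in each arm, and strictly above it wherever any subject's most related AE is *unlikely related*. No planned table is stated to separate the levels, although the protocol asks for a summary by relatedness.

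The size cannot be derived from the documents, and every rate used above is an assumption. The unchanged difference and the shrinking ratio both depend on balance between the arms. If *unlikely* events are unbalanced, the difference shifts by v₁ − v₀, and only a split would show it.

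No hypothesis test or efficacy result is affected. The gap is in descriptive safety reporting and is worth closing because the remedy is cheap.

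**What to change.** - In Table 14.3.2.1, show the number and percentage of subjects at each investigator relatedness level on the CRF, using the most related occurrence per subject.
- Add a possibly-related-or-related row for AEs and another for SAEs, beside the inclusive row.
- In SAP 4.9.2, state which definition applies to the related-SAE row and to Table 14.3.2.3, and repeat it in their titles or footnotes.
- The inclusive definition may be kept, provided it is labelled as including *unlikely related*.

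The cost is a few extra rows, some SAP wording and a small amount of programming. The change uses the investigators' existing causality judgements and needs no new data.
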